## ABSTRACT

Obesity is currently a pandemic. The treatment of patients affected by obesity is very complex and requires the synergy of a multidisciplinary team that addresses the problem in its different spheres. Among the available treatment options, surgery remains the most effective in the long term. Among surgical techniques, there are different types based on different mechanisms. Among them, hypoabsorptive techniques, which are the most effective, can lead to malnutrition and vitamin deficiencies, so the creation of a standardized score -similar to Clavien-Dindo- could be a simple, reproducible tool with sufficient clinical relevance to allow comparison of nutritional outcomes between different surgical techniques.

**Hypothesis:** The BARSCORE score will allow estimation of supplementation needs for vitamins, micronutrients and proteins after bariatric surgery.

**Objectives:** To validate a score in bariatric surgery that grades supplementation needs by relating them to patient characteristics and the proposed surgical technique.

**Methodology:** Observational, longitudinal, multicenter study. The study sample will consist of patients who underwent bariatric surgery between January 2015 and December 2021 in participating centers. Patients will be divided into three groups based on the surgery performed and the score will be applied. Subsequently, surveys will be conducted to evaluate the score and cases for applying the score. For statistical analysis, Spearman's correlation test will be used to verify the consistency of the score and a two-way ANOVA analysis to measure its concordance.

## INTRODUCTION

Morbid obesity is considered the great epidemic of this century. It is the leading cause of non-traumatic death in the Western population and is progressively affecting developing countries. In the latest epidemiological studies, it is estimated that in Spain more than 15% of the population is overweight, and approximately 5% suffer from morbid obesity.

The treatment of morbid obesity is multidisciplinary, ranging from changes in lifestyle habits and diet to surgery. Among all available therapeutic options, bariatric surgery is the only cost-effective long-term treatment for patients with morbid obesity. It offers better results than pharmacological treatments and lifestyle changes. Furthermore, it has been shown to reduce and improve comorbidities, improve quality of life, reduce the risk of cardiovascular diseases and mortality, and improve quality of life [1-3].

There are currently several standardized bariatric surgical techniques. These techniques can be restrictive such as vertical gastrectomy (VG), hypoabsorptive such as duodenal switch (DS) and single-anastomosis duodeno-ileal bypass with sleeve gastrectomy (SADI-S), or mixed such as gastric bypass (GBP). Their indication will depend on factors such as the patient's BMI, metabolic comorbidities, or the surgical team's experience, among others. All of them have proven to be safe in experienced teams, with mortality rates equal to or less than 0.5% and morbidity less than 10% [4-5].

Although postoperative risks are low, they must be considered along with the potential benefits of surgery on an individual basis and as accurately as possible in each case. This allows the decision to perform surgery to be made consensually with the patient based on objective data.

One of the main risks, especially of mixed and hypoabsorptive techniques, is the risk of malnutrition and vitamin deficiencies. This complication is recorded in the literature in a heterogeneous and non-comparable manner. Articles documenting levels of nutrients, vitamins, and trace elements in blood during follow-up after bariatric surgery are complex to assess since data collection is not performed in a standardized way and it is not specified whether blood levels are with or without supplementation or the supplementation dose received; making them non-uniform and difficult to compare with each other.

A classification based on the therapeutic effort needed to resolve nutritional deficits (similar to the concept of the Clavien-Dindo classification for short-term post-surgical complications) could have the advantage of simplicity, reproducibility, and sufficient clinical relevance to allow comparison between different surgical techniques. This score could be evaluated along with efficacy (amount of weight lost and resolution of comorbidities) and morbidity (short and long-term complications) to assess the pros and cons of each surgical technique for each patient profile [6-8].

The bariatric surgery, endocrinology, and nutrition teams from HUB, HCP, and VHG hospitals reached consensus on a score for predicting therapeutic effort in supplementation after bariatric surgery. The objective of the present study is to retrospectively validate its utility and reproducibility in patients operated on for vertical gastrectomy, gastric bypass, duodenal switch, and single-anastomosis duodenal switch with a minimum of two years of clinical and analytical follow-up.

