### **Specific Objectives**

1. Demonstrate the coherence of the score after comparing different types of surgical techniques with different complexity and their obtained score.
2. Verify concordance through responses obtained by investigators from each center in the case survey to apply the score.
3. Verify ease of application through the percentage of favorable responses obtained in the score evaluation survey by participating investigators from each center.

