### Procedure

1. **Patient recruitment:** Inclusion of patients in the multicenter online database.
2. **Patient stratification:** Division of patients into three groups according to the surgery performed (vertical gastrectomy, gastric bypass, and single and double anastomosis duodenal switch) and categorization of patients using the supplementation needs score.
3. **Determine score coherence:** Comparison of score results between different groups of surgical techniques based on their complexity using Spearman's correlation coefficient.
4. **Verify score concordance (reproducibility):** At least two investigators from each center will answer the case survey to apply the score. Subsequently, a two-way ANOVA analysis will be performed on the case survey after applying a normal distribution transformation of the percentage of correct answers.
5. **Verify ease of score application:** Response from at least two investigators from each center to a survey about the complexity and utility of the score, performing a descriptive analysis of the results.

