### **Primary Outcome Measures**

1. **Score Coherence** (Time Frame: Minimum 2 years post-surgery follow-up)
  - Spearman correlation coefficient between surgical complexity and BARSCORE score
  - Success criterion:  $p < 0.05$
2. **Score Concordance (Reproducibility)** (Time Frame: Single assessment after database completion)
  - Two-way ANOVA analysis of responses from different investigators on standardized cases
  - Success criterion:  $p < 0.05$
3. **Ease of Application** (Time Frame: Single assessment after database completion)
  - Percentage of favorable responses in evaluation survey
  - Success criterion: >70% favorable responses

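### Members of the teams that agreed the score may act as its case raters and survey respondents, which can inflate the ease-of-use percentage and the apparent agreement between raters

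*Combined protocol and SAP*

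**What the plan says.** The Introduction identifies who made the score: the surgery, endocrinology and nutrition teams of three hospitals "reached consensus on a score for predicting therapeutic effort in supplementation after bariatric surgery".

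The Procedure section then defines the two panels. Step 4, on concordance: "At least two investigators from each center will answer the case survey to apply the score". Step 5, on ease of application: "Response from at least two investigators from each center to a survey about the complexity and utility of the score". The Specific Objectives describe the ease result as the percentage of "favorable responses obtained in the score evaluation survey by participating investigators from each center".

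Both results are primary outcomes. Concordance is a "Two-way ANOVA analysis of responses from different investigators on standardized cases" with success at p < 0.05, and Procedure step 4 says it is run "after applying a normal distribution transformation of the percentage of correct answers". Appendix A supplies the answer key for 14 cases. Ease has the "Success criterion: >70% favorable responses".

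No section in the available text excludes those who agreed the score, asks for author status, or plans a separate or sensitivity analysis by it. Inter-center variability is a secondary outcome but is not tied to author status.

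**The concern.** People who negotiated the grade definitions are not ordinary users of them. The plan's own instruments show why this matters.

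- **Ease survey (Appendix B).** The first item asks how long the score took to understand, which means little for someone who helped to write it. The yes/no items ask whether it is simple, reproducible, logical, useful and beneficial, so authors would be judging their own product.
- **Case survey (Appendix A).** Answers are marked against a key, and some keyed grades need more than the written rules. The application notes in Appendix C require more than two years of follow-up, yet Cases 1, 4, 10 and 13 are at nine months, one year, one year and one and a half years, and each has a keyed grade. The same notes count need only from the third month, while Case 11 places the need somewhere in the first year. An author can settle such points from the consensus discussion; another user has only the text.

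The Expected Benefits section wants the score for comparison between techniques, surgeons and centers, so the results are meant to extend to users who did not write it. If authors and users are pooled, the reported ease and agreement may be better than independent users would show.

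**Working it through.** The plan gives no figure that can be reproduced here. It states no number of respondents, and no number of centers appears in the available text. What follows is an illustration under stated assumptions.

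**Inputs from the plan.** Three authoring hospitals (Introduction); at least two respondents per center (Procedure); threshold above 70% (Primary Outcome Measures); 14 cases (Appendix A).

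**Assumptions.** All three authoring hospitals take part. Each center supplies exactly two respondents, and all six at the authoring hospitals are authors. Each respondent gives one overall favorable or unfavorable verdict. The favorable rate is 95% among authors and 60% among others.

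**Ease: expected pooled percentage.** With K centers there are 2K respondents, and the expected share is (6 × 0.95 + (2K − 6) × 0.60) / 2K.

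- K = 6: (5.7 + 3.6)/12 = 0.775
- K = 10: (5.7 + 8.4)/20 = 0.705
- K = 20: (5.7 + 20.4)/40 = 0.6525, given as 65.2%

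**Ease: probability of exceeding 70%.** The numbers of favorable authors and favorable non-authors are independent binomials and are summed exactly.

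| Centers | Respondents | Favorable needed | All non-authors at 60% | Six authors at 95%, rest at 60% |
|---|---|---|---|---|
| 6 | 12 | 9 | 0.23 | 0.74 |
| 10 | 20 | 15 | 0.13 | 0.43 |
| 20 | 40 | 29 | 0.07 | 0.21 |

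**Ease: rate needed among non-authors.** If all six authors are favorable, the pooled figure reaches 70% when the non-author rate is (0.7 × 2K − 6)/(2K − 6). This is 2.4/6 = 40% at 6 centers, 8/14 = 57% at 10 and 22/34 = 65% at 20.

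**Sensitivity to the assumptions.** The expected result exceeds 70% when the author share is above (0.70 − non-author rate)/(author rate − non-author rate). With six authors the share is 6/2K = 3/K.

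- 95% against 60%: share above 0.10/0.35 = 0.286, so up to 10 centers
- The same rates with one author per authoring center, share 3/2K: up to 5 centers
- 85% against 60%: share above 0.10/0.25 = 0.40, so up to 7 centers
- 95% against 50%: share above 0.20/0.45 = 0.444, so up to 6 centers

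**Concordance.** A simulated rater-by-case two-way ANOVA on correct/incorrect answers to 14 cases (no transformation; 3,000 repeats; case difficulty normal with SD 1 on the logit scale) assumed accuracy on an average case of 95% for authors and 70% for others.

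| Centers | Raters | Mean % correct | P(p < 0.05), rater term | P(p < 0.05), case term |
|---|---|---|---|---|
| 6 | No authors | 67% | 0.05 | 0.89 |
| 6 | Six authors | 80% | 0.88 | 0.74 |
| 10 | No authors | 67% | 0.04 | 0.98 |
| 10 | Six authors | 75% | 0.89 | 0.95 |

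The percentage correct rises with authors in the panel. The p-value does not move one way: the rater term becomes significant more often and the case term less often. The plan does not say which term decides success.

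**The case against.** Several points on the other side are fair.

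- **Both criteria biased upward.** A reader might infer that author raters make both primary criteria easier to pass. That is supported for the ease threshold only. For concordance, authors plausibly raise the percentage correct and agreement, but neither is the stated criterion, and the two ANOVA terms move in opposite directions. This stands.
- **The threshold is passed with up to 10 centers.** A reader might infer this from the expected 70.5% at 10 centers. It is an expected value, not an outcome: under the same assumptions the chance of exceeding 70% there is 0.43, so failing is more likely than passing. This stands.
- **Authors will be the respondents.** The plan permits this but does not say it. The hospital abbreviations are not expanded in the available text, and a center list may lie in pages not available here. The Introduction also names teams, not individuals. This stands, so the claim is only that the plan can produce bias.
- **Scope of the claim.** The Hypothesis and Specific Objectives speak of investigators at the centers, not clinicians at large. That is true of the endpoint wording, but the Expected Benefits section implies wider use.
- **Existing mitigation.** Inter-center variability might expose a difference at authoring hospitals. Without a record of author status it could not be attributed to authorship.

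None of this supplies the missing exclusion, record or split analysis.

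**Conclusion.** The concern holds as a possible bias. The plan lets those who agreed the score supply data for two of its three primary outcomes and gives no means of seeing their influence. If the authoring hospitals participate and authors respond, the favorable percentage, the percentage correct and the agreement between raters can all be inflated. No direction can be claimed for the ANOVA criterion until the tested term is named.

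The size is unknown. The illustrated inflation of the ease result is large with few centers (17.5 percentage points at 6) and small with many (about 5 at 20). It depends wholly on the assumed number of authors and the assumed gap between authors and others.

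**What to change.** In Procedure, steps 4 and 5:

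1. Choose raters and respondents who took no part in the consensus, wherever such investigators exist, including at the three authoring hospitals.
2. Record author status (yes/no) for every respondent in both surveys.
3. Base the primary ease and concordance results on non-authors and show authors separately.
4. As a fallback, if non-authors are too few, report both groups separately and limit the conclusion to users who helped to develop the score. This is needed because, if only the three authoring hospitals took part and all six respondents were authors, there would be no non-author result.

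If the surveys have already been completed, author status can still be recorded and the split reported.

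The cost is one yes/no field and one divided table, or a different choice of existing investigators. The downside is fewer raters and less precision where authors cannot be replaced. For example, at a true rate of 60% the standard error is √(0.6 × 0.4/12) = 14 percentage points with 12 respondents and √(0.6 × 0.4/6) = 20 points with 6.

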## **HYPOTHESIS**

The BARSCORE score will allow estimation of supplementation needs for vitamins, micronutrients, and proteins after bariatric surgery.

The BARSCORE score will be a coherent score, so that more complex surgeries will have higher scores in the score with a Spearman correlation test with  $p < 0.05$ .

The BARSCORE score will be a score with a high level of concordance since different investigators from each center will score the presented cases in the same way, obtaining a two-way analysis of variance with  $p < 0.05$ .

The BARSCORE score will be an easy-to-apply score since it will obtain a percentage of favorable results greater than 70% in the score evaluation survey.

## **OBJECTIVES**

### **General Objective**

To validate a score in bariatric surgery that grades supplementation needs by relating them to patient characteristics and the proposed surgical technique.

### **Specific Objectives**

1. Demonstrate the coherence of the score after comparing different types of surgical techniques with different complexity and their obtained score.
2. Verify concordance through responses obtained by investigators from each center in the case survey to apply the score.
3. Verify ease of application through the percentage of favorable responses obtained in the score evaluation survey by participating investigators from each center.

## METHODS

### Study Design

Observational, multicenter, longitudinal study based on the medical records of a cohort of patients operated on for primary laparoscopic bariatric and metabolic surgery from January 2015 to October 2022, in participating centers.

### Procedure

1. **Patient recruitment:** Inclusion of patients in the multicenter online database.
2. **Patient stratification:** Division of patients into three groups according to the surgery performed (vertical gastrectomy, gastric bypass, and single and double anastomosis duodenal switch) and categorization of patients using the supplementation needs score.
3. **Determine score coherence:** Comparison of score results between different groups of surgical techniques based on their complexity using Spearman's correlation coefficient.
4. **Verify score concordance (reproducibility):** At least two investigators from each center will answer the case survey to apply the score. Subsequently, a two-way ANOVA analysis will be performed on the case survey after applying a normal distribution transformation of the percentage of correct answers.
5. **Verify ease of score application:** Response from at least two investigators from each center to a survey about the complexity and utility of the score, performing a descriptive analysis of the results.

### Study Population

**Target Population:** Patients undergoing primary minimally invasive bariatric surgery from the population area of all participating centers, between 18 and 65 years of age, in the period from January 2015 to July 2022.

### Inclusion Criteria:

- Patients operated on for primary laparoscopic bariatric surgery using vertical gastrectomy, gastric bypass, duodenal switch, or single-anastomosis duodenal switch (SADI-S) techniques
- Surgery performed between 2015 and 2022 in participating centers
- Minimum 2-year follow-up
- Available analytical control and evaluation by endocrinologist and dietitian/nutritionist

### **Exclusion Criteria:**

- Patients operated on for revisional surgery
- Patients with less frequent techniques such as single-anastomosis gastric bypass or intestinal bipartition
- Patients operated on via open approach or requiring conversion to open approach during surgery
- Patients with loss to follow-up

### **Experimental Treatment**

Primary laparoscopic bariatric or metabolic surgery.

### **Primary Outcome Measures**

1. **Score Coherence** (Time Frame: Minimum 2 years post-surgery follow-up)
  - Spearman correlation coefficient between surgical complexity and BARSCORE score
  - Success criterion:  $p < 0.05$
2. **Score Concordance (Reproducibility)** (Time Frame: Single assessment after database completion)
  - Two-way ANOVA analysis of responses from different investigators on standardized cases
  - Success criterion:  $p < 0.05$
3. **Ease of Application** (Time Frame: Single assessment after database completion)
  - Percentage of favorable responses in evaluation survey
  - Success criterion: >70% favorable responses

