### **Primary Analysis:**

1. **Coherence:** Spearman correlation test (significance:  $p < 0.05$ )
2. **Concordance:** Two-way ANOVA assuming normality and homoscedasticity (significance:  $p < 0.05$ )
3. **Ease of application:** Descriptive analysis with percentages (target: >70% favorable responses)

**Risk Factors:** Initial risk factors include sociodemographic data (age, sex, BMI), comorbidities, type of bariatric surgery, and surgical complications.

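### Coherence is declared on Spearman p < 0.05 alone: at 1,200 patients a |rho| of about 0.057 passes, and neither the hypothesised direction nor the technique steps enter the success rule

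*Combined protocol and SAP*

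**What the plan says.** Primary Outcome Measures, item 1, defines coherence by the "Spearman correlation coefficient between surgical complexity and BARSCORE score" and sets p < 0.05 as the success criterion. The Statistical Analysis Plan, under Primary Analysis, repeats this as "Spearman correlation test (significance" at p < 0.05) and adds nothing. Neither place gives a minimum rho, a confidence interval, the sidedness of the test or the required sign.

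The Hypothesis section says more. It predicts that "more complex surgeries will have higher scores in the score with a Spearman correlation test with" p < 0.05.

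The Procedure section, step 2, sets out the groups: "Division of patients into three groups according to the surgery performed (vertical gastrectomy, gastric bypass, and single and double anastomosis duodenal switch"). Step 3 then plans a "Comparison of score results between different groups of surgical techniques based on their complexity using" Spearman's coefficient. No section assigns complexity ranks to the techniques. The order sleeve, bypass, duodenal switch recurs, however, in the last paragraph of the Introduction, in the Procedure and in the Inclusion Criteria.

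Secondary Outcome Measures includes a description of supplementation needs by technique. Sample Size Determination sets a minimum of 1,200 patients, calls the study exploratory and says that the size of the expected differences is not known.

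**The concern.** The hypothesis is ordered and directional, while the success rule asks only whether the overall rank correlation differs from zero. Three things follow.

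- **Strength.** With 1,200 or more patients, almost any real association will be significant, so passing says little about how well the score separates the techniques.
- **Direction and steps.** Read literally, a significant negative rho would pass. More realistically, a positive rho can come from one contrast, such as sleeve versus bypass, with no rise or even a fall at the next step.
- **Ranks.** Spearman's coefficient needs a ranking of complexity, and the plan implies one without declaring it.

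Expected Benefits says the validated score will be used to compare techniques, surgeons and centers and to inform consent. A declaration of coherence that a near-zero correlation can earn is a weak basis for that.

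**Working it through.** **Inputs from the documents.** n is at least 1,200; alpha is 0.05; there are three technique groups and eight ordered grades (0, I, IIA, IIB, IIIA, IIIB, IV, V; Appendix C). Sidedness is not stated, so two-sided is assumed and one-sided is also shown. The 1,200 is not derived from power or an effect size, so there is no planned figure to reproduce.

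**Step 1: smallest significant rho.** The formula is r = t / √(t² + n − 2). For n = 1,200 two-sided, t = 1.962 on 1,198 degrees of freedom, so r = 1.962 / √(3.849 + 1,198) = 1.962 / 34.67 = 0.0566, and r² = 0.0032.

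- One-sided at n = 1,200: 0.0475.
- Two-sided at n = 2,000: 0.044. At n = 3,000: 0.036.
- Simulated null with three tied groups (480/480/240) and eight tied grades: 0.0567, so ties do not change the answer.
- Fisher-z 95% interval at rho = 0.0566, n = 1,200: 0.000 to 0.113.

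**Step 2: does the rule check the steps?** The documents give no grade distribution or group sizes, so everything in this step is assumed. n = 1,200, with groups of 400/400/400 or 600/480/120 (50/40/10%). Patients below grade II are split 0:I as 1:5. Patients at grade II or above are split IIA:IIB:IIIA:IIIB:IV:V as 15:10:7:3:3:2. Scenarios are defined by the share at grade II or above in sleeve/bypass/switch. The rank-based rule is rho > 0 with p < 0.05, and for both adjacent pairs a probability of superiority (ties counted half) above 0.5.

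| Shares | Current rule passes (equal; 50/40/10%) | Rank-based rule passes (equal; 50/40/10%) |
|---|---|---|
| 30/45/60%, clearly ordered | 100%; 100% | 99.6% to 100% across the two |
| 30/35/40%, small steps | 75%; 57% | 68%; 50% |
| 30/45/45%, flat top step | 97.9%; 99.8% | about half |

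For 30/45/40%, where the top step is reversed, the current rule passes 75.0% and 98.7% of datasets. It passes with an observed switch mean grade at or below bypass in 62.7% and 77.3%. Requiring both mean-grade steps to be positive cuts the pass rate to 12.3% and 21.4%.

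A separate simulation with other assumed grade distributions (groups 480/480/240) agrees. With sleeve equal to bypass and switch higher, mean rho is 0.19 and the current rule passes in 100% of runs. With bypass below sleeve and switch highest, mean rho is 0.14 and it passes in 99.9%.

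**Step 3: choice of step statistic.** The score is ordinal with heavy ties. On the clearly ordered 30/45/60% data, requiring differences in medians would pass only 0.7% and 0.3% of datasets, against 99.6% to 100% for the rank-based measure. The statistic must therefore be named.

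**The case against.** **The direction is stated.** The Hypothesis section gives it in the same sentence as the test, so a reader who infers that the plan has no direction is mistaken. What stands is that the two places defining success do not carry it over. The numerical effect is small: a significant negative rho occurred in 0.0% of simulated runs with a technique effect, and in about 2.5% with none.

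**The ranking is implied.** A reader might set the Procedure's order against the Introduction, where "These techniques can be restrictive such as vertical gastrectomy (VG), hypoabsorptive such as duodenal switch (DS") and related techniques come before mixed ones, and infer two competing rankings. The documents do not support that. The Introduction sorts by mechanism and ranks nothing, and every list of the operations as study groups or eligible techniques runs sleeve, bypass, switch. The gap is a missing declaration, and one sentence closes it.

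**A reversal is not expected.** The Introduction says "One of the main risks, especially of mixed and hypoabsorptive techniques, is the risk of malnutrition and vitamin deficiencies", and the Abstract says that "hypoabsorptive techniques, which are the most effective, can lead to malnutrition and vitamin deficiencies". The reversed scenario is a test of the rule and not a forecast.

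**Weak results would be seen.** The coefficient is itself the outcome measure, and needs by technique are a secondary outcome. This is true, but neither can change the pass or fail verdict.

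**The stricter rule is a choice and does not remove weak correlations.** Coherence could be read as an overall association, which Spearman's test does address. Also, with steps judged by mean grade, the revised rule still passes with rho below 0.10 in about 43% (equal groups) and 39% (50/40/10%) of the 30/35/40% datasets. That is why the size of rho has to enter the conclusion. Because the plan says magnitudes are unknown, a fixed minimum rho is left to the investigators.

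**Conclusion.** The concern holds in this form: success rests on p < 0.05 alone, which |rho| of about 0.057 meets at 1,200 patients, and the rule neither carries over the stated positive direction nor checks each technique step. The threshold follows from the plan's own n and alpha, assuming a two-sided test. The pass rates, including the 63% and 77% with the top step not rising, rest on assumed grade shares and group sizes and show only what the rule can let through. The documents do not support reading this as an absent direction, as contradictory rankings, or as evidence that the score will prove disordered. The analysis remains usable, but its success claim is stronger than its test, and the wording should be changed.

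**What to change.** 1. Declare the complexity ranks before analysis: sleeve < bypass < duodenal switch including SADI-S, for the investigators to confirm.
2. Define coherence as rho > 0 with p < 0.05, and both adjacent comparisons (bypass versus sleeve, switch versus bypass) in the predicted direction. Judge each step by the Mann-Whitney probability of superiority, ties counted half, above 0.5. Do not use medians.
3. Report rho and both step estimates with 95% confidence intervals, beside the planned by-technique distribution. Word the conclusion by the size of rho and not by significance alone.

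**Cost.** A few lines of text and no new data. Under the assumed 30/35/40% shares, the pass rate falls by 75 − 68 = 7 points with equal groups and 57 − 50 = 7 points with 50/40/10% groups. A flat top step still passes about half the time on direction alone, so the step intervals must be shown. The Timeline places the analysis in January to March 2025; if it has already been run, the added criteria should be labelled post hoc.

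### The primary ease-of-application outcome is declared met on any observed percentage above 70%, with no interval and only a floor of two respondents per center

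*Combined protocol and SAP*

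**What the plan says.** Under Primary Outcome Measures, item 3, the measure is "Percentage of favorable responses in evaluation survey", with "Success criterion: >70% favorable responses". The Hypothesis section says the score will be easy to apply because "it will obtain a percentage of favorable results greater than 70% in the score evaluation survey", so the observed percentage is itself the evidence for the claim.

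The analysis is lighter than that wording. The Primary Analysis section of the Statistical Analysis Plan gives "Descriptive analysis with percentages (target: >70% favorable responses". Step 5 of the Procedure asks for "Response from at least two investigators from each center to a survey about the complexity and utility of the score" and then for "performing a descriptive analysis of the results". No interval, test or null value is planned for this outcome. Sample Size Determination gives a number for patients (at least 1,200) and none for survey respondents.

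The text does not state how many centers take part. The Introduction says that "teams from HUB, HCP, and VHG hospitals reached consensus on a score", but it does not say that these three are the only participating centers.

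**The concern.** A pass/fail line on a primary outcome is being read from a point estimate whose precision is neither planned nor reported. The 1,200 patients add nothing here, because the data are investigators' opinions. If the panel is small, a few answers decide whether the outcome is met. A reader told that the criterion was met could not tell 5 of 6 from 50 of 60. Pooling items does not fully repair this, because one person's answers tend to agree and so carry less information than the same number of independent answers.

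At stake is one of the study's three validation claims. The score could be reported as shown to be easy to apply on data that are compatible with a true favorable rate well below 70%.

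**Working it through.** The plan gives no sample size, power or interval for this outcome, so there is no figure of its own to reproduce. The check is how the stated rule behaves.

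**Inputs**
- Rule: observed proportion above 0.70 (Primary Outcome Measures; Hypothesis).
- Floor: two respondents per center (Procedure, step 5).
- Assumption: number of centers. Three centers at the floor would give 3 × 2 = 6 respondents. Totals of 10, 20 and 40 are shown as a range.
- Assumption: within-respondent correlation of 0, 0.3 or 0.5 when items are pooled.
- Denominator: not defined in the plan, so both readings are shown.

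**A. Counting respondents.** With n respondents the smallest passing count is r = floor(0.7n) + 1. The chance of passing at true rate p is P(X ≥ r), with X binomial(n, p). The interval at a bare pass is the two-sided 95% Clopper-Pearson interval for r/n.

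Example, n = 6: r = floor(4.2) + 1 = 5, and at p = 0.6 the chance of passing is 6(0.6⁵)(0.4) + 0.6⁶ = 0.187 + 0.047 = 0.233.

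| Respondents | Needed | Passes at true 60% | Passes at true 70% | Exact 95% CI at bare pass |
|---|---|---|---|---|
| 6 | 5 (83.3%) | 23% | 42% | 36-99.6% |
| 10 | 8 (80%) | 17% | 38% | 44-97.5% |
| 20 | 15 (75%) | 13% | 42% | 51-91% |
| 40 | 29 (72.5%) | 7% | 44% | 56-85% |

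The 70% column stays near 40% at every size. That is a property of any cut-off and not a defect of this plan. What a small panel changes is the 60% column and the width of the interval.

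**B. Pooling items.** Six closed items from 6 respondents give 36 answers, and the rule needs floor(25.2) + 1 = 26. Simulating each respondent's answers as beta-binomial, a true 60% passes about 9% of the time at correlation 0, 21% at 0.3 and 25% at 0.5. Using only the five yes/no items (30 answers, 22 needed), the figures are 9%, about 20% and about 24%.

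The opposite error depends heavily on the denominator. A true 85% fails 22% of the time when 6 respondents are counted (1 − 0.776). With six pooled items it fails only about 1%, 8% and 12% at correlations 0, 0.3 and 0.5.

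**C. When a two-sided 95% exact interval lies wholly above 70%, counting respondents.** With all n favorable the lower limit is 0.025^(1/n), which is 54.1% at n = 6 and 69.2% at n = 10, so neither size can reach it. It takes 12 of 12, 19 of 20 or 34 of 40.

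**The case against.** **The respondents are not a sample.** Specific Objective 3 concerns the participating investigators themselves. If all of them answer, the percentage has no sampling error for that group. This stands for a claim limited to the group. The Hypothesis, however, makes a claim about the score, and a floor of two per center does not secure a full response. An interval also does not deal with who is asked: some respondents may come from the teams that wrote the score. The response rate helps a reader judge the first of these points, not the second.

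**The panel may be large.** The number of centers is not given and two is a minimum. At 40 respondents a true 60% passes only 7% of the time. This stands, so the size of the problem is conditional. A bare pass at 40 still has an interval of 56-85%, which is worth reporting.

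**The study calls itself exploratory and this analysis descriptive.** That explains the missing power calculation. It does not fit with a success criterion on a primary outcome; if the intent is descriptive, the wording should say so.

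**Stronger readings a reader might infer.** One is that the panel is known to be small; the documents do not say that. Another is that the rule will often reject a good score; the 22% failure rate at a true 85% rests on a per-respondent denominator that the plan does not state, and pooling brings it to about 1-12%. A third is that success should require the lower one-sided 95% limit to exceed 70%. That rule cannot be met with 6 respondents (0.05^(1/6) = 0.607), and it would fail a true 85% about 80% of the time with 10 respondents and 60% with 20. It would also call 9 of 9 or 10 of 10 a success while the two-sided interval, with lower limits of 66.4% and 69.2%, still includes 70%. Nothing in the plan calls for it.

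**Conclusion.** The point holds in limited form. The plan lets a bare percentage decide a primary outcome without stating its uncertainty. With an assumed 6 to 20 respondents, counted one each, a true 60% meets the criterion about 23% to 13% of the time, and a bare pass is compatible with true rates as low as 36% (5 of 6) or 51% (15 of 20). With 40 respondents the figures are 7% and 56%. If six items from 6 respondents are pooled, the false-pass rate is about 9% with independent answers and 21-25% under the assumed correlations. These sizes rest on an assumed number of respondents and assumed correlations. The absence of an interval beside a pass/fail criterion rests on the text alone. This is an inexpensive reporting improvement, and it does not invalidate the study.

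**What to change.** In Primary Outcome Measures, item 3, and in the Primary Analysis section:

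1. Report the number of respondents and the response rate among those invited.
2. State the denominator, and report the percentage with a two-sided 95% interval that treats the respondent as the unit: exact binomial if respondents are counted, or a respondent-level or cluster bootstrap interval if items are pooled.
3. Describe 70% as a descriptive target. If the observed percentage is above 70% but the reported interval includes 70%, write *observed above target, not confirmed*, and do not state that the hypothesis is demonstrated. Align the Hypothesis wording with this.
4. Do not replace the criterion with a one-sided lower-limit rule.

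The cost is a few lines of text and a record of who was invited; no patient data are needed. The ease statement becomes more cautious. With a small panel it will usually be descriptive only, and always so with 6 or 10 respondents counted one each.
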